5.4.5. Ibrutinib Dose Modification for Hepatic Impaired Subjects

Ibrutinib is metabolized in the liver and therefore subjects with clinically significant hepatic impairment at the time of Screening (Child-Pugh class B or C) are excluded from study participation. For subjects who develop mild liver impairment while on study (Child-Pugh class A), the recommended dose reduction for ibrutinib is to a level of 280 mg daily (two capsules). For subjects who develop moderate liver impairment while on study (Child-Pugh class B), the recommended dose reduction is to a level of 140 mg daily (one capsule). Subjects who develop severe hepatic impairment (Child-Pugh class C) must hold study drug until resolved to moderate impairment (Child-Pugh class B) or better. Monitor subjects for signs of toxicity and follow dose modification guidance as needed (Refer to [Appendix 9](#)).

5.5. Lenalidomide

All subjects in both phases of this study will receive lenalidomide and will follow guidelines for lenalidomide dosing and toxicity management.

5.5.1. Formulation, Packaging, and Storage of Lenalidomide

Lenalidomide (Revlimid[®]) will be supplied as capsules for oral administration by Celgene Corporation.

Lenalidomide will be shipped to the pharmacy at the study site in individual bottles or blister packs. Bottles or blister packs will contain a sufficient number of capsules to last for one cycle of dosing. Lenalidomide must be dispensed in the original packaging with the label clearly visible. **Only enough lenalidomide for 1 cycle of therapy may be provided to the subject each cycle.**

The Investigator or designee is responsible for taking an inventory of each shipment of lenalidomide received on the drug accountability form.

Lenalidomide should be stored at room temperature away from direct sunlight and protected from excessive heat and cold.

5.5.2. Lenalidomide Prescribing Information (applies to US sites only)

Lenalidomide (Revlimid[®]) will be provided to research subjects for the duration of their participation in this study at no charge to them or their insurance providers. Lenalidomide will be provided in accordance with Celgene Corporation's Revlimid REMS[™] program. Per standard Revlimid REMS[™] program requirements, all physicians who prescribe lenalidomide, and all research subjects enrolled into this trial, must be registered in, and must comply with, all requirements of the Revlimid REMS[™] program. All lenalidomide prescribers must be certified to prescribe lenalidomide and included on the Form FDA 1572. Study drug will be shipped on a per subject basis by the contract pharmacy (ie, Biologics, Inc.) to the clinical site. All subjects will be counseled through the Revlimid REMS[™] program with all pregnancy requirements, including the use of birth control and pregnancy testing before lenalidomide can be shipped to the site investigational pharmacy to dispense to the subjects. Only enough lenalidomide for one cycle of therapy will be supplied to the subject each cycle.

Pregnancy Testing

Refer to [Appendix 7](#).

5.5.3. Lenalidomide Drug Dispensing Requirements (applies to ex-US sites only)

In investigational studies, lenalidomide will be dispensed through a qualified healthcare professional (including but not limited to, nurses, pharmacists and physicians) and lenalidomide prescribers must be included on the Form FDA 1572. These healthcare professionals will be trained by Celgene or designee in requirements specific to counseling of subjects. Each site is

required to have two trained counselors at all times. Once trained, these healthcare staff will counsel the subjects prior to medication being dispensed to ensure that the subject has complied with all requirements including use of birth control and pregnancy testing (FCBP) and that the subject understands the risks associated with lenalidomide. This step will be documented with a completed Education and Counseling Guidance Document ([Appendix 8](#)), and no drug will be dispensed until this step occurs. Counseling includes verification with the subject that required pregnancy testing was preformed and results were negative. A Lenalidomide Information Sheet ([Appendix 8](#)) will be supplied with each medication dispense.

Pregnancy Testing

Pregnancy tests for females of childbearing potential. A female of childbearing potential (FCBP) is a sexually mature female who: 1) has not undergone a hysterectomy or bilateral oophorectomy; or 2) has not been naturally postmenopausal (amenorrhea following cancer therapy does not rule out childbearing potential) for at least 24 consecutive months (ie, has had menses at any time in the preceding 24 consecutive months).

Pregnancy tests must occur within 10–14 days and again within 24 hours prior to initiation of Cycle 1 of lenalidomide. FCBP with regular or no menstruation must have a pregnancy test weekly for the first 28 days and then every 28 days while on lenalidomide therapy (including breaks in therapy); at discontinuation of lenalidomide and at Day 28 post the last dose of lenalidomide. A FCBP with irregular menstruation must have a pregnancy test weekly for the first 28 days and then every 14 days while on lenalidomide therapy (including breaks in therapy), at discontinuation of lenalidomide and at Day 14 and Day 28 post the last dose of lenalidomide (see [Appendix 8](#)).

Counseling

All subjects must be counseled about pregnancy precautions, risks of fetal exposure and other risks. The counseling must be done on Day 1 of each cycle (or at a minimum of every 28 days) throughout the entire duration of lenalidomide treatment, including dose interruptions, and at lenalidomide discontinuation. The [Appendix 8 \(Section 3\): Education and Counseling Guidance Document](#) must be completed by a trained counselor.

5.5.4. Dosage, Preparation and Administration of Lenalidomide

The first dose of lenalidomide will be administered orally on Cycle 1 Day 1, of the Treatment Phase, after which lenalidomide will be self-administered daily by the subjects on Days 1-21 of each cycle.

Lenalidomide will be dosed 0-30 minutes before the rituximab infusion and at the same time as ibrutinib.

Lenalidomide should be administered with water at approximately the same time each day. The capsule should be swallowed intact and subjects should not attempt to chew capsules, open

capsules or dissolve them in water. Females of childbearing potential should not handle or administer lenalidomide unless they are wearing gloves.

If a dose of lenalidomide is missed, it should be taken as soon as possible on the same day. If a dose is missed for the entire day, it should not be made up.

Lenalidomide dosing during the Treatment Phase occurs on Days 1-21 each cycle followed by a mandatory 7-day drug-free interval. If a Day 1 (of any Cycle) is delayed due to scheduling, instruct the subject that lenalidomide dosing should not be initiated until Day 1 assessments can occur.

Treatment will continue until disease progression or other reason for treatment discontinuation as outlined in [Section 9](#).

Dose modifications for toxicity are outlined in [Section 5.5](#), [Table 6](#) and [Table 7](#).

For instructions regarding drug accountability and disposal/return of unused lenalidomide refer to the Pharmacy Manual.

5.5.5. Dose Delay, Reduction or Discontinuation of Lenalidomide

In order to initiate a new cycle of therapy with lenalidomide, the subject must have an ANC $\geq 1,000/\mu\text{L}$ and a platelet count $\geq 50,000/\mu\text{L}$ and no lenalidomide related Grade ≥ 3 toxicity on Day 1. If these two criteria are not met, the entire cycle with all drugs is to be delayed and a repeat assessment is to be performed per the Investigator's decision. The initiation of lenalidomide should be delayed until the subject meets the above criteria at which time the subject will initiate drug without dose modification. The initiation of lenalidomide may occur on any day of the cycle, but missed doses must be omitted. Omitted doses should not be made up, and lenalidomide dosing must end no later than Day 21 of any given cycle. Once a cycle has initiated, if lenalidomide must be held for toxicity during dosing, except for an AE of rash, lenalidomide will not resume until Day 1 of the subsequent cycle, provided the subject meets the cycle initiation criteria above, with dose adjustments as per [Table 6](#).

Treatment with lenalidomide should be withheld for any unmanageable, potentially study drug-related non-hematological toxicity that is Grade 3 or higher in severity and any hematologic toxicity as described in [Table 6](#). In the event the subject is diagnosed with a thyroid condition or experiences a drop in creatinine clearance to $\leq 60 \text{ mL/min}$, refer to [Table 6](#) for further instructions.

Any other clinically important events where dose delays may be considered appropriate by the Investigator must be discussed with the Medical Monitor.

Lenalidomide may be withheld for a maximum of 28 consecutive days for toxicity. Lenalidomide treatment should be discontinued in the event of a lenalidomide related toxicity lasting more than 28 days, unless approved by the Medical Monitor.

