1.14.3. Deep Venous Thrombosis

In the lenalidomide label ([Revlimid® USPI](#), February 2015) for the indication of multiple myeloma, there is a black box warning for deep venous thrombosis and pulmonary embolism. In patients with multiple myeloma receiving lenalidomide with dexamethasone, there is a significantly increased risk of deep venous thrombosis and pulmonary embolism.

As per the FDA label, venous thromboembolic events (predominantly deep venous thrombosis and pulmonary embolism) have occurred in patients with multiple myeloma treated with lenalidomide combination therapy and patients with myelodysplastic syndrome treated with lenalidomide monotherapy. A significantly increased risk of deep venous thrombosis and pulmonary embolism was observed in patients with multiple myeloma who were treated with lenalidomide and dexamethasone therapy (see label). It is not known whether prophylactic anticoagulation or antiplatelet therapy prescribed in conjunction with lenalidomide may lessen the potential for venous thromboembolic events, however thromboprophylaxis is recommended (see label). The decision to administer prophylactic measures should be done carefully after an assessment of an individual patient's underlying risk factors.

Since deep venous thrombosis can be clinically managed with anticoagulation, and the risk-benefit ratio for this study population would still be in favor of continued treatment to achieve an anti-tumor response, only deep venous thrombosis that is unresponsive to anticoagulation will be considered a DLT. This would also be consistent with other studies testing the ibrutinib and lenalidomide combination ([Christian ASH 2014](#)).

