5.2. Dose Limiting Toxicity (DLT) Definition

A DLT is defined as one of the following events that is possibly related to study drug:

Hematologic:

- Grade 4 neutropenia (ANC $<500/\text{mm}^3$) lasting for >7 days
- Life-threatening Grade ≥ 3 neutropenia (ANC $<1,000/\text{mm}^3$) with fever $\geq 38.3^\circ\text{C}$

- Grade 4 thrombocytopenia ($<25,000/\text{mm}^3$) that persists for ≥ 7 days, despite holding treatment
- Grade 3 thrombocytopenia associated with Grade ≥ 2 bleeding or requiring RBC or platelet transfusions

Non-Hematologic:

Any Grade 3 or higher non-hematologic adverse event with the clarifications noted below:

(Note: excludes rituximab infusion reactions)

- Grade 3 tumor lysis syndrome would be considered a DLT only if it requires dialysis.
- Grade 3 deep venous thrombosis would be considered a DLT only if it is unresponsive to anticoagulation
- Grade 3 rash that has not improved within 10 days to at least Grade 1 using a temporary drug hold of all study drugs and administration of up to 100 mg of prednisone PO or equivalent (with or without taper) and/or antihistamines PO daily
- Grade 3 infection is not a DLT, however an infection with life-threatening consequences or requiring urgent intervention (grade 4) will be considered a DLT
- Grade ≥ 3 nausea, vomiting, or diarrhea uncontrolled by maximal supportive care and persisting greater than 7 days
- Grade 3 fatigue persisting for greater than 7 days
- Treatment delay of any drug greater than 7 days for toxicity

In the Dose Escalation Phase, if a subject is non-compliant with the prescribed therapy or ends treatment within the first cycle for reasons other than study drug(s) related toxicity, ie, withdraws consent, they will be replaced. In addition, any subject that misses >7 doses of ibrutinib and/or lenalidomide for reasons other than AEs of rash will be replaced; subjects with AEs of rash that miss >10 doses of ibrutinib and/or lenalidomide will be replaced unless considered a DLT. Any subject that requires rituximab discontinuation during the first cycle per the guidance in [Section 5.6.4](#) will be replaced. Subjects with bulky tumors have an increased risk of TLS, and sufficient hydration and close monitoring of laboratory parameters (eg, a chemistry panel every 3 days) is recommended for this patient population. Investigators are encouraged to monitor subjects at high risk for TLS closely.

Table 4: Phase 1b Dosing Levels

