5.5.6. Dose Modification of Lenalidomide during a Cycle (applies to Days 1-21)

The dose of lenalidomide should be modified according to the dose modification guidelines in Table 6 if any of the following toxicities occur:

Table 6: Dose Modification or Interruption for Lenalidomide Toxicity during a Cycle

Toxicity	Intervention
Thrombocytopenia:	
 Grade 3 (decrease to <50,000/μL) associated with Grade ≥ 2 bleeding, OR Grade 4 (decrease to <25,000/μL) 
 Interrupt lenalidomide treatment for the remainder of the cycle Reduce the dose of lenalidomide by one dose level (5 mg) at the start of the next cycle. Do not initiate a new cycle until the subject meets cycle initiation criteria (see Section 5.5.5). Do not dose below 5 mg daily.
Neutropenia:	
 ANC <1,000/μL for > 7 days, OR ANC <1,000/μL with an associated temperature $\geq 38.5^{\circ}\text{C}$, OR ANC <500/$\mu$L 
 Interrupt lenalidomide treatment for the remainder of the cycle Reduce the dose of lenalidomide by one dose level (5 mg) at the start of the next cycle. Do not initiate a new cycle until the subject meets cycle initiation criteria (see Section 5.5.5). Do not dose below 5 mg daily.
Rash:	
 Any Grade desquamating (blistering) Grade 4 non-blistering Grade ≥ 3 
 For any Grade desquamating or Grade 4, discontinue lenalidomide permanently For Grade ≥ 3 rash, hold lenalidomide until rash improves to \leq Grade 1, then resume at original dose (for first episode) or lower dose as clinically indicated. Treatment with 20 mg prednisone PO or equivalent daily for 10 days (with or without taper) and/or antihistamines PO daily is recommended; discontinue allopurinol if rash is thought to be at least possibly related to allopurinol. During DLT observation period: If \geq Grade 3 rash has not improved to at least Grade 1 within 10 days using a temporary hold of study drugs and administration of up to 100 mg of prednisone or equivalent (with or without taper) and/or antihistamines daily, rash is considered a DLT. Outside of DLT observation period: see recommendations for Grade ≥ 3 rash above

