Venous thromboembolism Grade ≥ 3	
 Interrupt lenalidomide treatment for the remainder of the cycle Initiate therapeutic anticoagulation – see Section 6.1.2.3. Resume lenalidomide without dose modification at the start of the next cycle if the benefit of therapy on this study outweighs the risk for bleeding.
Hyperthyroidism or hypothyroidism	
 Interrupt lenalidomide treatment for the remainder of the cycle

Toxicity	Intervention
	
 • Evaluate etiology and initiate appropriate therapy • Reduce the dose of lenalidomide by one dose level (5 mg) at the start of the next cycle. Do not initiate a new cycle until the subject meets cycle initiation criteria (see Section 5.5.5). Do not dose below 5 mg daily.

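### Phase 1b: a non-rash lenalidomide toxicity hold starting on Days 2-14 of Cycle 1 triggers replacement under Section 5.2 as written, even when the subject had a DLT

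*Protocol*

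**What the plan says.** **Hold rule.** Lenalidomide is dosed on Days 1-21 of a 28-day cycle (Protocol 5.5.4). Under Protocol 5.5.5, after an in-cycle hold for toxicity, "except for an AE of rash, lenalidomide will not resume until Day 1 of the subsequent cycle". Section 5.5.6, which applies to Days 1-21, adds: "The dose of lenalidomide should be modified according to the dose modification guidelines in Table 6 if any of the following toxicities occur". Table 6 gives the instruction "Interrupt lenalidomide treatment for the remainder of the cycle" for Grade 3 or higher venous thromboembolism. It gives the same instruction for other Grade 3/4 non-hematologic toxicity attributed to lenalidomide, and for certain cytopenias, thyroid disorders and reduced creatinine clearance.

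**DLT definition (Protocol 5.2).** Grade 3 or higher non-hematologic events are DLTs, subject to listed clarifications. One is "Grade 3 infection is not a DLT". Grade 3 tumor lysis syndrome counts only if dialysis is needed. For thrombosis, Section 1.14.3 gives the intent: "only deep venous thrombosis that is unresponsive to anticoagulation will be considered a DLT". The same list makes this a DLT: "Treatment delay of any drug greater than 7 days for toxicity".

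**Replacement (Protocol 5.2).** A first sentence replaces subjects who are non-compliant or who end treatment in Cycle 1 for reasons other than drug-related toxicity. The next says "any subject that misses >7 doses of ibrutinib and/or lenalidomide for reasons other than AEs of rash will be replaced", and then, for rash, "subjects with AEs of rash that miss >10 doses of ibrutinib and/or lenalidomide will be replaced unless considered a DLT".

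**Analysis sets.** Neither Protocol 10.2 nor SAP 2.1 defines a DLT-evaluable set. SAP Table 5 provides only a listing of DLTs.

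**The concern.** The hold rule and the replacement rule work against each other inside the DLT window. A toxicity serious enough to stop lenalidomide in the first two weeks forces more than 7 missed doses, and more than 7 missed doses forces replacement. The protection for toxicity in the first replacement sentence is not carried into the second, and the DLT exception is attached only to rash. Taken as written, the rule can replace a subject for the very event that Phase 1b exists to detect.

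A second conflict depends on interpretation. Section 5.2 does not define treatment delay. If it includes an in-cycle hold, the delay criterion makes a DLT of events that the same section exempts.

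MTD or RP2D is a Phase 1b primary endpoint (SAP 1.2.1) and is decided by very small counts. Under Protocol 5.1, 3 DLTs in 9 subjects mean that the MTD is exceeded, whereas 2 in 9 allow escalation.

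**Working it through.** **1. Missed doses.** Inputs: last dosing day 21 (Protocol 5.5.4); no restart before the next cycle (5.5.5); Cycle 2 Day 1 is Study Day 29 (5.1). For a first missed dose on Day d of Cycle 1, missed doses = 21 - d + 1 = 22 - d, and calendar days to Cycle 2 Day 1 = 29 - d. The plan states no such figure, so there is none to reproduce.

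| First missed day | Missed doses | Days to Cycle 2 Day 1 | More than 7 doses? |
|---|---|---|---|
| 2 | 20 | 27 | yes |
| 8 | 14 | 21 | yes |
| 14 | 8 | 15 | yes |
| 15 | 7 | 14 | no |
| 21 | 1 | 8 | no |

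The replacement limit is passed exactly when 22 - d > 7, that is, on Days 2-14. If a delay counted all calendar days, including the planned rest week, the 7-day limit would be passed for every start on Days 2-21.

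**2. Two worked cases.**

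- *Exempted event.* A Grade 3 deep venous thrombosis responds to anticoagulation; the first missed dose is on Day 10. Table 6 stops lenalidomide for the rest of the cycle: 22 - 10 = 12 missed doses. Under the thrombosis clarification it is not a DLT. Under the delay criterion it is one, if a delay includes a hold. Under the replacement clause the subject is replaced. Tumor lysis syndrome without dialysis and Grade 3 infection follow the same path when lenalidomide is held for them, which under Table 6 requires attribution to lenalidomide.
- *Non-exempted event.* A Grade 3 non-hematologic event with no clarification of its own, attributed to lenalidomide, has its first missed dose on Day 8. It is a DLT. It also costs 22 - 8 = 14 doses for a reason other than rash, so the replacement clause applies with no exception.

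**3. Effect on the count.** With 2 other DLTs in a full cohort, counting the held subject gives 3 in 9 (MTD exceeded). Replacing that subject with one who has no DLT gives 2 in 9 (dose passes), if the replaced subject's event is dropped.

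**4. Illustration.** The documents give no hold rates, so these are assumed. With DLT rate p per subject and q = 1 - p, the 3+3+3 pass probability is the sum of four paths:

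- no DLT in the first 3: q^3
- 1 in the first 3, none in the next 3: 3pq^5
- 1 in each of the first two groups of 3, none in the last: 9p^2q^7
- 2 in the first 3, none in the next 6: 3p^2q^7

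Enumerating all outcomes for 9 subjects gives the same values. Let p be the rate of other DLTs and h the rate of holds starting on Days 2-14, mutually exclusive. Counting held subjects as DLTs gives rate p + h. Replacing them and dropping their events gives p/(1 - h).

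| p | h | Counted: rate | Pass | Replaced: rate | Pass |
|---|---|---|---|---|---|
| 0.10 | 0.05 | 0.15 | 90.0% | 0.105 | 95.8% |
| 0.10 | 0.10 | 0.20 | 80.9% | 0.111 | 95.2% |
| 0.10 | 0.20 | 0.30 | 58.3% | 0.125 | 93.6% |
| 0.20 | 0.05 | 0.25 | 70.0% | 0.211 | 78.7% |
| 0.20 | 0.10 | 0.30 | 58.3% | 0.222 | 76.2% |
| 0.20 | 0.20 | 0.40 | 36.3% | 0.25 | 70.0% |

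A third option, keeping held subjects in the denominator as DLT-free, leaves the rate at p: 96.4% for p = 0.10 and 80.9% for p = 0.20. That is more lenient than replacement.

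**The case against.** **Delay may mean a late cycle start.** Section 5.5.5 mostly uses delay for cycle start and speaks of holding within a cycle; Table 6 speaks of interrupting. The specific only-if wording for thrombosis and tumor lysis syndrome would naturally govern a generic criterion in the same list. This is a fair reading, and under it exempted events are not DLTs. But usage is not uniform: Sections 5.4.3 and 5.5.5 also use dose delays loosely. A reader might infer that Section 5.2 definitely calls every such hold a DLT; the documents support that only on one reading. The delay criterion also sits under the non-hematologic heading, so it does not clearly reach cytopenia holds, although the replacement clause does.

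**Replaced need not mean erased.** A reader might infer that replacement deletes an observed DLT. The protocol does not say so. Section 5.1 defines the MTD by the share of subjects enrolled in a cohort who have a DLT, and stops enrollment at the third DLT. Where Section 5.6.4 wants both non-DLT status and replacement, it states both. This stands, and it limits the claim: the text orders replacement and leaves the fate of the event open.

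**Committee discretion.** The Dose Level Review Committee weighs all safety data (Section 5.1). That softens the consequence but does not correct the rule.

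**The hold trigger is narrower than it looks.** Section 5.5.5 directs withholding for unmanageable Grade 3 or higher non-hematologic toxicity, and the last row of Table 6 requires attribution to lenalidomide. Brief fatigue or controlled diarrhea may never be held. Thrombosis has its own row and is the clearest case.

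**Cohort 1 is not evidence.** A reader might take its 12 treated but 7 evaluable subjects as a sign of this problem. No reasons are given for the other 5, Section 5.1 names disease progression as a reason for not completing the window, and Cohort 1 preceded the amended DLT rules.

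**Conclusion.** The concern holds in limited form. It is certain that a non-rash toxicity hold with first missed dose on Days 2-14 costs 8-20 doses and meets the replacement clause, and that this clause lacks the DLT exception given to rash. It is conditional that the same hold is also a DLT for exempted non-hematologic events; that needs treatment delay to include in-cycle holds. One classification can move a cohort between 2 and 3 DLTs in 9. The pass probabilities illustrate sensitivity under assumed rates and do not estimate what happened in this trial.

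A reader of Protocol 1.17.2 might also infer that the 25 mg cohort has yet to be run. SAP 1.7.2 reports that it was under way when Phase 2 began, so a protocol clarification may come too late for some or all of its subjects. The reporting remedy can still be carried out at the final analysis.

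**What to change.** 1. **Protocol 5.2, replacement.** Apply the DLT exception to both the more-than-7-dose and the more-than-10-dose clauses, so that no subject with a DLT is replaced out of the count.
2. **Protocol 5.2, delay criterion.** State that a rest-of-cycle interruption required by Table 6 for an exempted event type does not by itself meet this criterion, which then refers to a delayed start of the next cycle. Subjects so held without a DLT may be replaced as under-exposed, but each is shown to the Dose Level Review Committee. Keeping them in the denominator as DLT-free would be too lenient: a subject held from Day 2 has taken one lenalidomide dose.
3. **SAP DLT listing.** Show every Phase 1b subject with more than 7 missed Cycle 1 doses, with reason and DLT status. Give each cohort's DLT count twice: with toxicity-held subjects counted as DLTs, and with them replaced.

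The cost is a short wording change, one added listing, and a DLT count that may be slightly less favourable. Phase 2 sample size and the ORR analysis do not change.
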